### 1.1. Version 4.0 Summary of Changes (13-March-2024):

Change Made	Location in Protocol
Sponsor contact information updated	Section 2.0 Contact Information, Section 3.0 Protocol Approvals
Interim analysis related text added	Synopsis, Section 7.2.2 Rationale for Interim Analysis, Section 9.1 Overall Study Design, Section 9.2 Number of Participants, Section 10.2 Participant Withdrawal Criteria, Section 15.2 Sample Size Determination, and Section 15.5 Interim Analysis
Footnote “f” was revised to remove “serum” from the alcohol screening text. The site’s standard for alcohol screening will be utilized.  An “X” was added to the Day 5 (Post-Study) weight measurements assessment to align with the corresponding text in Section 11.7.5 (Day 5 (Post-Study))	Table 5 Schedule of Assessments
Reference to the site’s smoking policy removed	Section 11.3.3 Smoking Restrictions
The caloric intake of standard meals was increased to accommodate the needs of lactating women (average of ~300 extra calories per day).	Section 11.5.1 Standard Meal
The prestudy screening window has been modified from 2 weeks to 4 weeks, which aligns with the Duration of Treatment text (Synopsis and Section 9.1 (Overall Study Design)) of 4 to 5 weeks.	Section 11.7.1 Prestudy Screening <del>Day -14</del> <del>Day -28</del> to Day -1, Table 5 Schedule of Assessments (Footnote “a”)
The predose safety labs and serum pregnancy test window was modified from 24 hours predose to 24-48 hours predose.	Section 11.7.2 (Predose (Prior to Day 1 Morning Dosing))
Last sentence was removed to clarify that all study medication will be dispensed while participants are domiciled.	Section 12.1 Study Drug
The calculation for M/P has been added.	Synopsis, Section 15.4 Pharmacokinetic Analysis

## 1.2. Version 3.0 Summary of Changes (26-May-2023):

Change Made	Location in Protocol
Clinical site information removed. Project Manager information updated. CRO project manager information combined.	Section 2.0 Contact Information
Site information removed and placeholders added	Synopsis and Investigator's Agreement Statement
Study center(s) field updated to “One (1) to 2 sites”, Country field updated, and Study period (years) field dates updated	Synopsis
Inclusion criterion #4 updated for consistency purposes and to include “acceptance of bottle feeding”. Inclusion criterion #9 updated to include vaping.	Section 10.1.1 Inclusion Criteria
Herbal products allowed to increase breast milk production updated.	Section 11.2 Prior and Concomitant Medications
Added text indicating acceptance of bottle feeding prior to study start. Added text related to breast feeding restrictions if a participant discontinues early.	Section 11.3.5 Breast Feeding
“Clinical research unit” text added and SAE reporting window clarified to align with Appendix B text.	Section 14.2.9 Reporting Adverse Events

### 1.3. Version 2.0 Summary of Changes (04-October-2022):

Change Made	Location in Protocol
Added text related to the benefits of breastfeeding compared to the risks of interruption of breastfeeding, including the potential for changes in milk supply and difficulty re-establishing breastfeeding after the study is completed.	Section 7.2.1 Benefits and Risks of Breastfeeding and Section 9.4.1 Potential Risks
Clarified the window prior and concomitant medication is 14 days prior to dosing (Day 1) and throughout the poststudy.	Section 11.2 Prior and Concomitant Medications and Section 14.1.6.9 Adverse Event and Concomitant Medication Assessment
Updated pre-dose safety lab and serum pregnancy sampling window extension to 24hrs predose instead of 12hrs predose.	Table 5 Schedule of Assessments and Section 11.7.2 Predose (Prior to Day 1 Morning Dose)
Added “serum pregnancy to have a sensitivity of at least 25 mIU/L.”	Section 14.1.6.7 Pregnancy Screen
Clarified the window for AEs and concomitant medications should be collected only through post study .	Section 14.1.6.9 Adverse Event and Concomitant Medication Assessments Section 14.2.8 Recording Adverse Events
Clarified serious adverse event information will be collected from time of informed through the poststudy visit .	Section 14.2.8 Recording Adverse Events
Clarified the vital signs <0 hours timepoint (pre-dose) acceptable time window may be performed up to 12 hours predose .	Appendix A: Time Window for Serial Assessments

## 4. SYNOPSIS

Name of Sponsor/Company: SCYNEXIS, Inc.						
Name of Investigational Product: Ibrexafungerp						
Name of Active Ingredient: Ibrexafungerp						
Protocol Number: SCY-078-121	Phase: 1	Country: US				
Title of Study: An Open-Label Pharmacokinetic Study in Healthy Lactating Women after Two Oral Doses of Ibrexafungerp Administered on a Single Day						
Study center(s): One (1) to 2 sites						
Studied period (years): Estimated date first patient enrolled: July 2023 Estimated date last patient completed: July 2024						
Objectives: Primary Objective: 

To determine whether ibrexafungerp is excreted in breast milk and if so, to characterize ibrexafungerp pharmacokinetics (PK) in the breast milk and plasma of lactating women.

 Secondary Objectives: 

To calculate the potential infant exposure to ibrexafungerp if lactating women are treated with ibrexafungerp.

To characterize the safety and tolerability of ibrexafungerp in lactating women.

						
Study Design: Ibrexafungerp is approved in the United States as a single day, two-dose therapy for women with vulvovaginal candidiasis (VVC). This is a Phase 1 study designed to determine whether this dose of ibrexafungerp is excreted in breast milk, and if so, to characterize ibrexafungerp PK in the breast milk and plasma of lactating women. Participants will receive a single day of twice daily (BID) 300-mg (2 x 150-mg) oral ibrexafungerp doses given 12 hours apart (Q12H). Participants will receive both doses on site. Participants will be admitted to the clinic on Day -1, and may be discharged on Day 5, after the 108-hour procedures are completed, at the discretion of the Investigator.						

Product, Dose, and Timing	Study Day	

Ibrexafungerp 300-mg BID on Day 1	1	

 
Safety will be monitored with laboratory and clinical evaluations: vital signs, physical examinations, and the collection of adverse events (AE) and concomitant medications. Breast milk and plasma PK
			Product, Dose, and Timing	Study Day	Ibrexafungerp 300-mg BID on Day 1	1
Product, Dose, and Timing	Study Day					
Ibrexafungerp 300-mg BID on Day 1	1					

samples will be obtained at selected intervals and time points pre-dose and post-dose for determination of ibrexafungerp concentrations.

An interim analysis will be performed after 5 subjects have completed the study.

**Number of participants (planned):**

Up to 10 healthy lactating females who are at least 10 days postpartum with a fully established milk supply and are between the ages of 18 and 50 years at the time of screening. Participants who discontinue or are discontinued may be replaced to ensure that an adequate number of participants to achieve the study objectives, complete the study.

**Investigational Product, Dosage, and Mode of Administration:**

The study drug, ibrexafungerp citrate salt tablets, will be provided as oral 150-mg tablets, by the Sponsor.

All participants will receive ibrexafungerp in two 300-mg (2 x150-mg tablets) oral doses given Q12H with food.

Ibrexafungerp citrate salt tablets will be stored at room temperature in a secure and locked location in the clinical research unit.

**Duration of Treatment:**

The duration of study participation from pre-study through post-study safety monitoring will be approximately 4 to 5 weeks for participants.

**Criteria for evaluation:**

**Pharmacokinetics:**

Breast milk will be obtained up to 108 hours post dose and blood samples will be obtained starting pre-dose the Day 1 morning dose until 108 hours post first dose of study drug for determination of ibrexafungerp concentrations. Sample time points are as follows:

- Breast Milk: complete expression of milk from both breasts (using a standard electric breast pump) will be obtained at the following timepoints and intervals: pre-dose, 0-2, 2-4, 4-8, 8-12, 12-18, 18-24, 24-36, 36-48, 48-72, and 72-108 hours post first dose of study drug.
- Plasma samples will be obtained at the following timepoints: 0 hours (prior to first dose), and at 2, 6, 8, 12 (prior to second dose), 24, 36, 48, 72, and 108 hours post first dose of study drug for determination of ibrexafungerp in plasma concentrations. The 12-hour samples will be taken prior to the second dose of ibrexafungerp.

The following plasma pharmacokinetic parameters: area under the curve (AUC), peak plasma concentration ( $C_{max}$ ), time to peak plasma concentration ( $T_{max}$ ), plasma clearance or apparent oral clearance (CL/F), apparent volume of distribution ( $V_d$ ), and terminal half-life ( $t_{1/2}$ ) for ibrexafungerp following oral administration of the VVC dosage regimen for ibrexafungerp will be determined for both breast milk and plasma concentrations.

The daily infant dosage (total drug present in milk and consumed by the infant per day) will be calculated:

- *Daily Infant Dosage (mg/day) =  $\Sigma$  (total drug concentration in each milk collection multiplied by the expressed milk volume in each milk collection)*

The Milk Plasma ratio (M/P) will be calculated.  $M/P = AUC_{0-24} \text{ milk} / AUC_{0-24} \text{ plasma}$ .

The calculation of M/P should be based on AUC and on multiple time points over 24 hours and not just a single point in time.

The relative infant dose (the percent of the weight-adjusted maternal dosage consumed in breast milk over 24 hours) will be calculated:

- *Relative Infant Dose = Infant Dosage (mg/kg/day)/Maternal Dosage (mg/kg/day) multiplied by 100*

The PK of ibrexafungerp plasma and breastmilk will be assayed using validated LC-MSMS methods.

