### **8.2. Secondary Objectives**

- To calculate the potential infant exposure to ibrexafungerp if lactating women are treated with ibrexafungerp.
- To characterize the safety and tolerability of ibrexafungerp in lactating women.

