## 10. SELECTION AND WITHDRAWAL OF PARTICIPANTS

### 10.1. Participant Selection Criteria

#### 10.1.1. Inclusion Criteria

A female will be included in the study if she meets the following inclusion criteria if the participant:

1. is a healthy lactating woman aged 18 to 50 years, inclusive, at Screening.
2. is at least 10-days postpartum after uncomplicated delivery with a full milk supply established. (There is no specific length of time postpartum).
3. is actively breastfeeding or expressing breast milk.
4. is willing to temporarily discontinue breast feeding their infant before the Day 1 morning dose through to 108 hours after the first dose (approximately 4.5 days) AND has the ability to pump breast milk and to provide a reserve for infant feeding, with acceptance of bottle feeding, prior to the study.

OR

has decided to discontinue breastfeeding permanently but has not yet started weaning their infant with acceptance of bottle feeding for the infant. Participants must have an adequate milk supply (if pumping at least 3 to 4 times a day) as milk composition changes during the weaning process.

*Note: Care should be taken to ensure that participants have not discontinued breastfeeding an infant in order to participate in the study.*

*Note: Alternative infant nutrition (previously stored breastmilk or infant formula) should be available for feeding the infant from study Day 1 through 96 hours after the second dose (108 hours after the first dose).*

*Note: A lactation specialist will be available for participant support during the study.*

5. is willing to fully express breast milk from both breasts during the duration of the milk collection portion of the study. Participants must be able to express milk from each breast at each pumping session using an electric breast pump.
6. has a Body Mass Index (BMI)  $\leq 34 \text{ kg/m}^2$  at the screening visit. BMI is calculated by taking the participant's weight in kg and dividing by the participant's height in meters, squared.
7. is judged to be in good health based on medical history, physical examination, vital sign measurements, and laboratory safety tests (all within laboratory normal ranges or changes outside the normal range judged to be clinically non-significant by the investigator) performed at the screening visit and prior to administration of the initial dose of study drug.
8. has no clinically significant abnormality on electrocardiogram (ECG) performed at the screening visit.

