5.7 Pharmacokinetic Analysis

5.7.1 Plasma and Breast milk Concentrations

In displays of plasma and breast milk concentration summary statistics (and in PK analyses), all plasma concentrations below the limit of quantification (BLQ) of the assay will be treated as “0” if they occur before the first measurable or after the last measurable concentration, and will be set as missing for data points in between two measurable concentrations. If a sample is missing or the value is not reportable and is between two measurable concentrations, the value at that time point will be left blank for the analysis and reported as either Not Reportable (NR) or No Sample (NS).

Individual participant plasma and breast milk ibrexafungerp concentrations, actual breast

milk and blood sampling dates and times, actual volume of breast milk collected at each time interval, actual dosing information (actual time and date of dosing, and actual dose taken) will be presented by participant in data listings.

Ibrexafungerp concentrations in plasma and in breast milk measured over time will be displayed graphically for individual participants and for all participants in the PK population and will be summarized descriptively based on nominal times. Linear and semi-log plots of geometric mean (SD) and individual ibrexafungerp concentration versus time profiles will be displayed. These linear and semi log plots will be generated separately for time restricting up to 24 hrs and for complete study duration (0-108 hrs). For geometric mean concentration-time profile plots, the nominal PK sampling time will be used, for individual concentration-time profile plots, the actual PK sampling time will be used.

The daily infant dosage (total drug present in milk and consumed by the infant per day) will be calculated as follows:

- Calculated Daily Infant Dosage (mg/day) = Σ (total drug concentration in each milk collection multiplied by the expressed milk volume in each milk collection)

The Milk Plasma Ratio (M/P) will be calculated. $M/P = AUC_{0-24} \text{ milk} / AUC_{0-24} \text{ plasma}$.

The calculation of Milk plasma ratio (M/P) should be based on AUC and on multiple time points over 24 hours and not just a single point in time.

Milk plasma ratio (M/P) = $AUC_{0-24} \text{ milk} / AUC_{0-24} \text{ plasma}$

The relative infant dose (the percent of the weight-adjusted maternal dosage consumed in breast milk over 24 hours) will be calculated:

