For determination of AUC_{0-inf}, if the percentage of extrapolated AUC is more than 20% of AUC_{0-inf} from t_{last} to infinity, then individual AUC_{0-inf} result will be listed but flagged as not reliable calculation. AUC_{0-inf} for these flagged subjects will not be included in descriptive statistics table.

The following plasma ibrexafungerp pharmacokinetic parameters will be calculated: area under the curve (AUC), peak plasma concentration (C_{max}), time to peak plasma concentration (T_{max}), plasma clearance or apparent oral clearance (CL/F), apparent volume of distribution (V_d), and terminal half-life (t_{1/2}).

The following PK parameters of ibrexafungerp in breast milk will be calculated: AUC

for the different collection periods, C_{av} based on AUC derived from collections at different time points above; total milk concentration data will be used to calculate C_{max} , C_{min} and T_{max} . The C_{av} is calculated as follows.

$$C_{av} = \text{AUC}_{0-24} / 24\text{h}$$

Plasma and breast milk PK parameters for individuals will be listed and summarized descriptively.

Plasma and breast milk concentrations and PK parameters will be summarized using descriptive statistics. Summary statistics for PK parameters except for T_{max} will be described by n, arithmetic mean (mean), arithmetic mean SD, arithmetic CV%, geometric mean, geometric SD, geometric CV%, min, median and max. For T_{max} , summary statistics will be described by n, median, min and max. For $t_{1/2}$, harmonic mean and pseudo SD will also be presented. CV% will be displayed in one decimal place.

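### Daily Infant Dosage is described as drug the infant consumes but is computed from pumped volume, so it and Relative Infant Dose scale with maternal output; a volume-standardised estimate should sit beside it

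*Protocol*

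**What the plan says.** The secondary objective is "To calculate the potential infant exposure to ibrexafungerp if lactating women are treated with ibrexafungerp" (Protocol 8.2). The endpoint serving it, Daily Infant Dosage in mg/day, is introduced in the Protocol Synopsis (Criteria for evaluation, Pharmacokinetics) with the words "The daily infant dosage (total drug present in milk and consumed by the infant per day) will be calculated". It is calculated as the sum of "total drug concentration in each milk collection multiplied by the expressed milk volume in each milk collection". Protocol 15.4 repeats this, and SAP 5.7.1 carries the same definition and formula: "The daily infant dosage (total drug present in milk and consumed by the infant per day) will be calculated as follows". Relative Infant Dose takes the infant dosage as its numerator.

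No infant drinks the milk in question. Protocol 11.3.5 stops breastfeeding from before the first dose through Day 5, and Protocol 13.2 bars giving the infant any milk expressed after the pre-dose pumping. Protocol 13.2 records the date, time and volume of milk expressed.

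On eligibility (Protocol 10.1.1):
- Criterion 2 asks for a full milk supply and adds: "There is no specific length of time postpartum".
- Criterion 3 accepts active breastfeeding or expressing.
- Criterion 4 admits women who are stopping permanently, provided weaning has not begun: "Participants must have an adequate milk supply (if pumping at least 3 to 4 times a day) as milk composition changes during the weaning process".

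SAP 5.7.2 already plans an average milk concentration over 24 hours: "The C_{av} is calculated as follows", followed by AUC0-24 divided by 24 h.

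**The concern.** The label and the formula describe two different quantities. The formula gives the drug leaving the mother in pumped milk. The label gives the drug entering one infant. They agree only if everything expressed would be fed to one infant and equals what that infant would drink. Neither document states this assumption.

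Eligibility does not secure it. Neither a full nor an adequate supply is given as a volume. Nothing requires exclusive breastfeeding, and nothing excludes mothers feeding more than one infant. The Protocol also treats supply as something that can change: 7.2.1 and 9.4.1 name altered supply as a risk of interrupting breastfeeding, and 11.2 may allow products taken to raise milk production.

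The objective concerns potential exposure when lactating women are treated. A low reported infant dose could reflect little milk pumped rather than little drug transferred. The summary table in SAP 5.7.1 shows infant dosage, relative dose and M/P, with no volume planned beside them. The study may also stop after five women if their data are judged sufficient (Protocol 15.5, SAP 5.9), so one unusual volume can carry weight.

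**Working it through.** The documents state no infant dose and no milk volume, so there is no figure of the plan's own to reproduce. The check is how the planned formula behaves.

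**Inputs from the documents.** Daily Infant Dosage (DID) = Σ CᵢVᵢ. The collections within 24 h are 0-2, 2-4, 4-8, 8-12, 12-18 and 18-24 h. The per-day sum is taken here over these six. Up to 10 women are planned, with an interim analysis after 5.

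**Assumptions, not in the documents.** One fully fed infant takes 800 mL/day (range shown: 500 to 1000). Concentrations are identical for every woman, set arbitrarily at 20, 60, 100, 90, 130 and 110 ng/mL; they cancel in the ratios. Volume is spread over the collections in proportion to their length.

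**Step 1: proportionality.** If every Vᵢ is multiplied by f, then Σ Cᵢ(fVᵢ) = f Σ CᵢVᵢ. This needs no assumed volume.

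**Step 2: illustration.** The time-weighted concentration is (20×2 + 60×2 + 100×4 + 90×4 + 130×6 + 110×6)/24 = 2360/24 = 98.33 ng/mL.

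| Expressed volume (mL/day) | DID (mg/day) | Ratio to 800 mL |
|---|---|---|
| 200 | 0.0197 | 0.25 |
| 400 | 0.0393 | 0.50 |
| 500 | 0.0492 | 0.625 |
| 800 | 0.0787 | 1.00 |
| 1000 | 0.0983 | 1.25 |
| 1600 (two infants fully fed) | 0.1573 | 2.00; 1.00 after dividing by 2 |

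**Step 3: Relative Infant Dose.** It equals (DID / infant kg) / (maternal mg/kg/day) × 100. At fixed weights and maternal dose, the factor f passes through unchanged.

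**Step 4: group mean.** Suppose all other women express exactly one infant's intake (ratio 1) and one woman has ratio f. The arithmetic mean is (n − 1 + f)/n and the geometric mean is f^(1/n).

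| n | f | Arithmetic | Geometric |
|---|---|---|---|
| 5 | 0.5 | (4 + 0.5)/5 = 0.90 | 0.87 |
| 5 | 2 | (4 + 2)/5 = 1.20 | 1.15 |
| 10 | 0.5 | (9 + 0.5)/10 = 0.95 | 0.93 |
| 10 | 2 | (9 + 2)/10 = 1.10 | 1.07 |

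**Step 5: behaviour after the change.** If the time-weighted 98.33 ng/mL stands in for Cav and intake is set at an illustrative 150 mL/kg/day, every woman in Step 2 gets 98.33 × 150 = 14,750 ng/kg/day, or 0.01475 mg/kg/day, whatever she pumped. At 200 mL/kg/day the figure is 0.01967 mg/kg/day.

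**The case against.** The strongest reply is that the design selects for high output and measures it well. Full supply is stated repeatedly. Women stopping permanently must not have begun weaning, must have an adequate supply and are described as pumping at least three to four times a day. Both breasts are emptied completely at each collection. No text suggests that partial feeders or mothers of twins are expected. This stands as mitigation: it narrows the low-volume route without closing it, and does nothing about more than one infant.

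Second, drug transfer is reported without volume. Milk concentrations, Cmax, AUC, Cav and M/P are summarised, and SAP 5.7.2 calls the milk-to-plasma AUC0-24 ratio of primary interest. Interval volumes are listed per woman, so a low dose due to low volume could be traced. This also stands. A reader might infer that the study's measure of transfer is itself confounded by pumping; it is not, because only the two derived dose endpoints carry the volume term. Listings allow a recalculation afterwards but do not prespecify one.

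Third, for a partial feeder the planned value may be right for her own infant, and the objective does not name a fully breastfed infant. That is fair: the figure is too low only as an estimate for a fully breastfed one.

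Fourth, a reader might infer a large error by comparing assumed pumped volumes with 150 mL/kg/day: 350 mL and a 9 kg infant give 38.9 mL/kg/day (3.9-fold under), while 1200 mL from a mother of twins set against one 4.5 kg infant gives 266.7 (1.8-fold over). The documents do not support that range. They supply none of its inputs, and it mixes infant weight with volume: at 4.5 kg the same 350 mL is 77.8 mL/kg/day, or 1.9-fold under. It also implies 150 × 9 = 1350 mL/day for one older infant, more than the 1200 mL assigned to twins. Against 800 mL/day, 350 to 400 mL is 2.3- to 2.0-fold under.

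**Conclusion.** The point holds in a limited form. Daily Infant Dosage is labelled as infant consumption but calculated from maternal output, and it and Relative Infant Dose move one-to-one with pumped volume at fixed concentration. That proportionality follows from the formula alone. The factors 0.50 and 2.00 describe a woman expressing half of one infant's intake and a woman fully feeding two. The group shifts of 0.90 or 1.20 (n = 5) and 0.95 or 1.10 (n = 10) assume one such woman among others who match exactly one infant's intake.

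The size and direction in this trial cannot be known, because no volumes are given and the two routes pull in opposite directions. A reader might conclude that the planned endpoint is invalid and should be replaced. The documents do not support that: it rests on measured volumes, is prespecified, and is a legitimate estimate once its assumption is stated. A standardised estimate relies on an outside intake figure instead, so the two belong side by side.

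**What to change.** In the Protocol Synopsis, Protocol 15.4 and SAP 5.7.1:

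1. Keep the planned sum, but label it the amount of drug excreted in expressed milk (mg), with a note that reading it as infant dose assumes all expressed milk is fed to one infant. In the summary table, show each woman's total 0-24 h expressed volume beside it.
2. Add a prespecified standardised estimate: infant dosage (mg/kg/day) = milk Cav (AUC0-24/24 h) × a stated intake per kg for a fully breastfed infant, with a higher-intake case. The sponsor should justify both values and the infant age they apply to. The 150 and 200 mL/kg/day used above are illustrative assumptions, not from the documents.
3. Report Relative Infant Dose on this basis alongside the planned one. The standardised estimate is already in the mg/kg/day units that Relative Infant Dose needs.
4. Within the lactation history already taken (Protocol 14.1.1), record the number of infants fed and whether feeding is exclusive or partial.

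The cost is wording changes, one or two extra table rows and a minor data item, with no added samples, visits or participants. The downside is that the added estimate depends on a stated intake assumption.
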